In the somewhat likely event that the interaction between time point and treatment is not significant, we can directly test for treatment efficacy by comparing the effect of treatment on the treated vs. untreated structures. We expect that the model estimate for Treated or Untreated clause will be significant at p<0.05 level, favoring the treated clauses, demonstrating that treatment was effective and ruling out maturational effects.

$$\begin{aligned} \text{Likelihood of a Correct Production} &= \text{TestPoint} * \text{TreatedOrUntreated} \\ &\quad + (1|\text{item}) + (\text{clause type} |\text{subject}) \\ \text{Structural Sensitivity} &= \text{TestPoint} * \text{TreatedOrUntreated} \\ &\quad + (\text{clause type} |\text{subject}) \end{aligned}$$

Aim 2. Determine whether the influence of delivery method (illustrated syntax stories or recast therapy) on dose delivered (number of exposures to the target) is of sufficient magnitude that changes in child outcomes are observed when treatment is delivered by caregivers.

We will first determine whether dose differs across the two at-home conditions. We will carry out an unpaired two-tailed t-test comparing the estimated dose delivered for each condition. We anticipate that the two conditions will differ and that the distributions will show low degrees of overlap (p<.05, d>.5).

To test the key question in Aim 2, we will test for a dose by test point or dose by treatment condition by test point interaction for stories at home and recasts at home conditions. Well-matched groups at pretest will be evident if the two conditions do not differ at pre-test. If one treatment condition is more effective than the other, this should be evidenced by an interaction between test point and treatment contrast effects that are significant at the p<.05 level; if, as we hypothesize, dose is a critical component of this difference, a two- or three-way interaction between time and dose or between time, treatment and dose will be observed. We would interpret the two-way interaction as indicating that dose, rather than treatment is critical for obtaining the key outcomes. A three- way interaction suggests that the delivery method modifies the effectiveness of the total dose.

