$$\begin{aligned} \text{Likelihood of a Correct Production} &= \text{TestPoint} * \text{TreatmentCondition} * \text{EstimatedDose} \\ &\quad + (1|\text{item}) + (\text{clause type} |\text{subject}) \\ \text{Structural Sensitivity} &= \text{TestPoint} * \text{TreatmentCondition} * \text{EstimatedDose} \\ &\quad + (\text{clause type} |\text{subject}) \end{aligned}$$

In the event that the interaction between time point and treatment is not significant, we can directly test for treatment efficacy by comparing the effect of treatment on the treated or untreated structures. We expect that the model estimate for Treated vs. Untreated clause will be significant at p<0.05 level, favoring the treated clauses, demonstrating that treatment was effective and ruling out maturational effects.

$$\begin{aligned} \text{Likelihood of a Correct Production} &= \text{TestPoint} * \text{TreatedOrUntreated} \\ &\quad + (1|\text{item}) + (\text{clause type} |\text{subject}) \\ \text{Structural Sensitivity} &= \text{TestPoint} * \text{TreatedOrUntreated} \\ &\quad + (\text{clause type} |\text{subject}) \end{aligned}$$

Power Analysis for Production

Power analyses were carried out using Monte Carlo simulation (5,000 iterations) via SAS 9.4 and PROC GLIMMIX using residual pseudolikelihood estimation of a binary logistic mixed effects model with item responses (n=20) nested within tests (n=4 representing test point and clause type repeated measures) that are nested within children (n=120) who have been randomly assigned to treatment conditions, counterbalanced across the 2 clauses. Random effects are included for items within clauses, as well as four correlated child-level random effects (i.e., for each of the four repeated measures). A single model was used to estimate power in alignment with the overall design of the study in which children are randomly assigned to one of FOUR conditions. Power for the more focused models described above can be inferred from the power estimates for the treatment contrasts below. By adopting this randomization scheme and model design, we retain the ability to test unplanned contrasts that go beyond the planned analyses for the Aims if we so chose (e.g., recasts in the lab vs. recasts at home) in order to carry out secondary analysis associated with cost effectiveness, dose, or home environment.

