Test scores were simulated based on means and standard deviations of pretest and posttest scores from a previous study. Pretest scores for both clauses were sampled from a Normal distribution with $M=3.0$ and $SD=2.5$, rounding to the nearest integer, with a minimum score of 0 and maximum score of 7 items correct (corresponding to the >40% correct study eligibility criteria). Posttest scores for untreated clauses were sampled from a Normal distribution with a correlation of .90 with pretest scores and $M=3.0$ and $SD=2.5$, rounding to the nearest integer, with a minimum score of 0. Posttest scores for treated clauses were sampled from a Normal distribution with a correlation of .90 with pretest scores, rounding to the nearest integer, with a minimum score of 0, and $M=5.5$ and $SD=4.0$ for the syntax stories at home condition ($ES=+1.0$), $M=4.0$ and $SD=4.0$ for the parent recasts condition ($ES=+0.4$), $M=6.0$ and $SD=3.5$ for the syntax stories in the lab condition ($ES=+1.2$), and $M=8.0$ and $SD=3.5$ for the lab recasts condition ($ES=+2.0$).

Based on the above effect size estimates, power for detecting main effects in Aim 1 exceeds .95 for the syntax stories at home, syntax stories in the lab, and lab recasts. Power is .61 for detecting main effects of parent recasts (i.e., the effect of parent recasts would need to exceed .50 to be detected with 80% power). Power for treatment effect contrasts is .75 to detect differences in syntax stories at home and parent recasts effects, .90 to detect differences in parent recasts and syntax stories in the lab effects, and .99 to detect differences in parent recasts and lab recasts effects. Other contrasts (e.g., syntax stories at home vs. syntax stories in the lab) have power less than 80% if the expected effect sizes hold true (i.e., +1.0 vs. +1.2); differences in effects would need to exceed 0.35 logits (2 raw score points) in order reach statistical significance with 80% power.

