The influence of dose (Aim 2) was simulated by predicting different dose distributions for each condition. These distributions were simulated and then we randomly sampled from the distribution for each case. Hypothesized distributions of dose lead to substantial changes in the result, and thus we make our method of construction these distributions clear here. We assume that a minimum dose is achieved during the training visits (home condition) or by attending at least 1 session (lab condition) for all children. The two in-lab conditions are highly similar and both assume that 25% of participants attend between 1 and 12 sessions, 25% attend between 12 and 16, and the remainder have perfect attendance. This is a conservative estimate based on attendance data from our summer camp study.

The two at-home conditions require slightly more explanation. We assume for recasts that the first quartile has a dose of up to 1 recast/5 min for 60 min per week. The next quartile extends up to 1 recast/5 min for 120 min per week. The third quartile ranges up to a dose of 1 recast every 3 min for 120 min per week and the last quartile assumes target delivery. Similarly, syntax stories at home escalates from reading 1x/week to reading 2x/week to reading 4x/week (as asked) to reading 1 syntax story daily as the maximum. Several families in the pilot data for the syntax stories read the provided syntax stories daily.

Table 1. Hypothesized dose delivered by condition, in quartiles

	Recasts in lab	Stories in lab	Recasts at home	Stories at home
minimum	60	60	60	60
1st quartile	768	768	96	240
median	912	930	192	460
3rd quartile	960	960	320	960
maximum	1008	960	960	1680

Next the gain obtained from each dose was estimated by multiplying the dose provided by a value drawn from a uniform distribution ranging from .0005 to .006, to account for the fact that some children will be more responsive to any given dose than others. Finally, the gain was added to the pretest scores to yield posttest values. Simulations were checked to ensure that final post-test means and standard deviations for the treated structure were in line with estimates for post-test gains used for Aim 1 simulations. Planned statistical analysis were carried out over the simulated data and these simulations were repeated 1000 times.

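### Aim 2 judges which home treatment is more effective from a model that holds delivered dose fixed, so any arm difference carried by dose drops out

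*Protocol*

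**What the plan says.** All references are to the Protocol, under Statistical Design and Power.

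- **Effectiveness rule (Analytic Approach, Aim 2).** "If one treatment condition is more effective than the other, this should be evidenced by an interaction between test point and treatment contrast effects", at p<.05. The Aim 1 text uses the same wording.
- **Key dose question (Aim 2).** The stated key test is dose by test point, or dose by treatment by test point. On the first of these: "We would interpret the two-way interaction as indicating that dose, rather than treatment is critical for obtaining the key outcomes".
- **Dose by arm (Aim 2).** A t-test compares estimated dose between the home arms: "We anticipate that the two conditions will differ and that the distributions will show low degrees of overlap".
- **Equations (Aim 2).** The first outcome model is TestPoint × TreatmentCondition × EstimatedDose. The second is TestPoint × TreatedOrUntreated, with no arm term. It is introduced by: "In the event that the interaction between time point and treatment is not significant, we can directly test for treatment efficacy". Aim 1 has a dose-free TestPoint × TreatmentCondition model, but it is written for the lab arms.
- **Definition of dose (Data Reduction, Estimated Dose).** Sessions reported by families, times the share documented on recordings, times the content observed in transcribed sessions.
- **Power (Power Analysis for Production).** "Power for the more focused models described above can be inferred from the power estimates for the treatment contrasts below". And: "Power for treatment effect contrasts is .75 to detect differences in syntax stories at home and parent recasts effects". That model is described without dose. A separate dose simulation reports .93 for dose and time.

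**The concern.** Estimated dose is a consequence of assignment. Once it is in the model, the test point by treatment term is the difference between home arms at a fixed dose. If dose is entered uncentred, it is the difference at dose zero, below the hypothesised minimum of 60. Either way it is not the difference between the arms as randomised.

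The protocol's hypothesis is that the home arms differ because stories deliver more exposures. If that is true, the term named as evidence of relative effectiveness should be near zero even though children assigned to stories do better. The dose t-test and the dose by test point result would still be reported, so the pathway would not be hidden. What would be missing is the randomised home-versus-home comparison. The treated-versus-untreated follow-up is keyed to a test point by treatment result that, for Aim 2, only the dose-conditioned model supplies.

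The dose slope would also carry a causal reading that the design cannot support. The Potential Benefits section expects benefit to vary with how faithfully parents implement treatment, so dose may track family engagement or child responsiveness.

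**Working it through.** **Inputs.** Pretest Normal(3.0, 2.5), rounded and limited to 0-7. Home post-test means 4.0 (recasts) and 5.5 (stories), SD 4.0, pre-post correlation .90. Table 1 home doses (minimum, quartiles, maximum): recasts 60/96/192/320/960; stories 60/240/460/960/1680. In the dose simulation, gain is formed by "multiplying the dose provided by a value drawn from a uniform distribution ranging from .0005 to .006", with the same distribution in every arm. Sample size is 30 per arm (120/4, the power model) or 35 per arm (planned completers). Assumptions: two-sided .05, and linear interpolation of dose between quartiles.

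**1. The stated .75.** SD of change = √(2.5² + 4.0² − 2×.90×2.5×4.0) = √4.25 = 2.06. For a 1.5-item difference with 30 per arm, closed-form power is .80. Simulating with the stated rounding and limits, without dose, gives .70-.72 on raw change and .75-.76 on change in empirical logits. So .75 is consistent with a dose-free contrast. The match is rough: the logit version gives .97 for the contrast stated as .90.

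**2. Difference as assigned, under the dose simulation.**
- Mean dose, recasts at home: (78 + 144 + 256 + 640)/4 = 279.5.
- Mean dose, stories at home: (150 + 350 + 710 + 1320)/4 = 632.5.
- Mean gain per exposure: (.0005 + .006)/2 = .00325.
- Arm difference in gain: (632.5 − 279.5) × .00325 = 353 × .00325 = 1.15 items.

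Because the gain per exposure has the same distribution in both arms, the true arm difference at fixed dose is zero. All 1.15 items run through dose.

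**3. What each model reports.** Simulated trials, 30 and 35 per arm. Percentages are the share of trials with p<.05. Dose is centred unless stated.

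| Analysis | Arm × test point, no dose | Arm × test point, dose in model |
|---|---|---|
| Change score | 1.15-1.20 items; 85-91% | 0.00 items; about 5% |
| Change score, binomial item noise added | 34-39% | about 5% |
| Change score, noise SD 1.12 added, robust errors | 1.12-1.13 items; 61-69% | about 0 items; about 5% |
| Binomial model, errors clustered by child | 0.35 logits; 78-85% | −0.01 logits; 6-8% (uncentred: 0.09 logits; 11-13%) |
| Logistic mixed model, subject intercept | 0.35-0.38 logits; 34-42% | −0.01 to −0.03 logits; 0-8% |

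The noise SD of 1.12 is 2.5 × √(2 × (1 − .90)). The dose t-test is significant in 97-99% of trials. Dose by test point in the full model, 30 per arm, has power .94 (change score) or .97 (clustered binomial), close to the stated .93; with the SD 1.12 noise it is .66.

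**4. Check against the protocol's own home gains.** Here the gain per exposure is rescaled by arm.
- Nominal gains 1.0 and 2.5: 1.0/279.5 = .0036 and 2.5/632.5 = .0040 per exposure. The difference is 1.5 items without dose and +0.16 to +0.18 at fixed dose, significant in 5-7%.
- Gains after the stated floor and cap, 1.25 and 2.57: .0045 and .0041 per exposure. The difference is 1.3-1.4 items without dose and −0.18 to −0.20 at fixed dose, significant in 5-11%.

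**5. The interpretation rule.** A dose by test point interaction shows that children who received more exposures gained more. It cannot set dose against treatment, because assignment is what moves the mean dose from about 280 to about 630.

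**The case against.** Aim 2 is declared as a dose question, and its equation matches that question. The dose t-test tests arm to dose, and dose by test point tests dose to outcome. The text calls dose a component of the arm difference, which suggests that a dose-free comparison comes first. The four-arm power model has no dose and gives power for exactly the home contrast. On this reading, one equation was simply not written. In context, treatment may also mean delivery method at equal dose, since the next sentences concern method modifying the effect of dose. The power section itself concedes that dose and delivery approach are confounded, and it never attaches .75 by name to the dose-conditioned term. The follow-up is optional. Finally, simulated power for the dose-free test is unstable, and adding binomial noise to scores whose SDs already describe observed tests partly double-counts error.

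Much of this is fair. The dose analysis is legitimate and should stay, a dose-free test may have been intended, and the detection rates should not be read as properties of the planned model. But no dose-free home comparison is written as the Aim 2 test, while a rule for declaring one home treatment more effective is. The sentence on power covers all the focused models, which include the dose-conditioned one. Even if treatment means method at equal dose, non-randomised dose does not support the causal contrast.

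**Conclusion.** The concern holds. As written, Aim 2 takes relative effectiveness from a term that excludes the hypothesised pathway. Two results are stable across every method tried: children assigned to stories lead by about 1.15-1.5 items, and the dose-conditioned arm term is small (−0.20 to +0.18 items with dose centred), reaching significance in at most about 13% of trials. Power for the dose-free test is not stable (34-91%), and nothing here rests on it.

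The calculations assume interpolated Table 1 doses and the protocol's gain model. They approximate the planned mixed model: treated clause only, no item effects. If delivery method also strongly changes the gain per exposure, the fixed-dose term would not be near zero, but it would still not be the difference between arms as randomised.

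**What to change.** - Add TestPoint × TreatmentCondition without dose for the two home arms as randomised, in the form of the Aim 1 model. Name it as the Aim 2 test of relative effectiveness and as the trigger for the treated-versus-untreated follow-up.
- Keep the dose model, with dose centred, or use a mediation analysis from arm through dose to gain with its assumptions stated, for the declared dose question.
- Describe the dose slope as an association and remove the words that set dose against treatment.
- State that .75 refers to the dose-free home contrast and .93 to dose by time.

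The cost is one extra model and some rewording. Randomisation, data collection and sample size are unchanged. The price is a more cautious dose claim and possibly a less powerful primary comparison: in the logistic mixed model under the protocol's dose simulation, 34-42% for the dose-free term against 85-99% for dose by time.

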****Updated to add changes in inclusionary criteria**

****Updated July 15, 2025 – Includes statistical analysis plan.**

Human Subjects Involvement, Characteristics, and Design

The study is a Phase I clinical trial that employs a randomized parallel design. We plan to enroll 160 children diagnosed with Developmental Language Disorder and their caregivers who will provide services to approximately half of these children. We predict that 15% of the children (N=20) will be lost to follow-up, thus we enroll 160, in order to have 140 children complete the entire study and meet the planned enrollment goals. Children will be randomly assigned to one of four treatment conditions, thus we expect 35 participants per condition. Research will be carried out at the University of Delaware and the University of Maryland College Park.

Children with Developmental Language Disorder (N = 160)

Inclusionary & Exclusionary Criteria:

- Age: 4-7 years old
- Primarily English speaking: Less than 20% exposure to another language, per parent report
- Document poor syntax skills: standard score below 85 on the DELV-NR composite, a dialect neutral assessment (Seymour, Roeper, de Villiers, & De Villiers, 2005).
- Nonverbal IQ within typical range: t-score at or above 35 on the DAS, matrices subscale, (Elliott, 2007).
- Hearing within the typical range: Pass screening using SoundScouts (Gumbie et al., 2018; Mealings et al., 2020) or provide reports of passing a hearing screening at school or in a pediatrician's office. *Due to COVID and limitations on in person activities, treatment may proceed even if these reports are not obtained if no one has concerns about hearing and we will track/follow up with families to obtain a clear hearing screening within 12 months of completion of intervention. Documentation of how many children did not complete hearing screenings will be retained and inform interpretation of data.
- No diagnosis of Autism: Cutoff score of 15 on the SCQ, (Rutter, Bailey, & Lord, 2003)
- No diagnosis of significant sensory-motor concerns or significant psychiatric disorders per parent report
- Able to benefit from treatment:
 - Score below 60% correct on experimenter developed elicited production probes of passives and object relative clauses
 - Producing simple transitive sentences (SVO) and MLU of 2.5 on 100 utterance language sample

Caregivers of Children with DLD (N=160)

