Simulations that include dose indicate power of .93 for models that include dose and time. Effects of treatment, dose, and power combined are not detectable because this estimation of dose confounds the distribution of dose with treatment delivery approach, as we hypothesize in the strategy. It suggests that three-way interactions will only be detectable if the delivery method modifies the benefit obtained from each exposure to the target form.

Power Analysis for Eye Tracking

Power analyses were carried out using G*Power (Faul, Erdfelder, Lang, & Buchner, 2007). Our preliminary data focused on eye-movements during a single test point, thus we do not have relevant estimates of fixation changes at multiple time points or following interventions. Consequently, we based our sample size on power analyses for production ($n=120$) and calculated the smallest changes in Structural Sensitivity that will be detectable with varying levels of power.

In our preliminary data ($n=15$), children with DLD revealed $M = 0.02$ and $SD = 0.17$ in the late window. With the proposed sample size, effect sizes of $d=.30$ will be detectable with 80% power, $d=.34$ with 90% power, and $d=.42$ with 99% power. These correspond to increases in Structural Sensitivity of $M=.05$, $M = .06$, and $M = .07$ respectively. For reference the TD children in our Preliminary Data have a Structural Sensitivity score that is $M=.29$ larger than that of the children with DLD. Based on this benchmark, improvements across time points that are 17-24% in magnitude would be detectable in the current design. This suggests that this study is adequately powered to detect relatively small changes in linguistically mediated fixations.

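### Aim 2 would read a dose-by-test-point interaction as showing that dose and not method matters, although home dose is not randomised and a non-significant three-way term does not show equal benefit per exposure

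*Protocol*

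**What the plan says.** Under Analytic Approach, Aim 2, the protocol fits test point × treatment condition × estimated dose in the two caregiver-delivered arms. It attaches a meaning to each term:

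- **Test point × treatment.** A more effective method should appear as an "interaction between test point and treatment contrast effects that are significant at the p<.05 level".
- **Test point × dose.** "We would interpret the two-way interaction as indicating that dose, rather than treatment is critical for obtaining the key outcomes".
- **Three-way term.** A three-way "interaction suggests that the delivery method modifies the effectiveness of the total dose".

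Under Data Reduction, estimated dose is the product of family-reported sessions, the share of sessions documented by recordings, and the rate observed in transcripts. The section on potential benefits expects benefit to vary by child and by how faithfully parents implement the treatment.

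Under Power Analysis for Production, each simulated child's gain is dose times a draw from a uniform distribution on .0005 to .006, for either method. Power is given as .93 for models with dose and time. Of the combined effect the protocol says: "Effects of treatment, dose, and power combined are not detectable because this estimation of dose confounds the distribution of dose with treatment delivery approach". It adds that a three-way interaction is detectable only if method changes the benefit of each exposure, and gives no power for that case.

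**The concern.** The sentence draws an either/or conclusion, and neither half is supported.

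**Crediting dose.** Children are randomised to method and deliverer, not to number of exposures. Home dose depends on what caregiver and child do afterwards. If a family or child characteristic raises both exposures and gain, the dose slope is positive even when exposures do nothing. The protocol documents wide variation in delivery ("Several families in the pilot data for the syntax stories read the provided syntax stories daily"). It does not document confounding, but nothing in the design excludes it.

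**Excluding method.** If a recast and a story exemplar differ in value, the plan leaves it to the three-way term to show this. When that term is non-significant and the dose term is significant, the wording discards method. That treats a failure to detect a difference as evidence of equality.

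Aim 2 concerns what happens when caregivers deliver treatment, and the protocol expects its results to inform how treatment is provided. A conclusion that exposure count matters and method does not would bear directly on that.

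**Working it through.** **Inputs from the protocol**

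- Home dose (minimum, first quartile, median, third quartile, maximum; Table 1): recasts 60, 96, 192, 320, 960; stories 60, 240, 460, 960, 1680.
- Gain = dose × U(.0005, .006). Pretest is Normal(3.0, 2.5), rounded and limited to 0–7, with 20 items per test.
- Sample: the power section has items and tests "nested within children (n=120) who have been randomly assigned to treatment conditions", which is 120/4 = 30 per arm. The design section says "thus we expect 35 participants per condition". Both sizes were used.
- α = .05, taken as two-sided.

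**Assumptions.** Doses are uniform between quartiles. Recast gain is multiplied by a ratio k. Observed scores are binomial with 20 items. Gain is regressed on dose, arm and dose × arm. Only the treated clause is simulated.

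**Step 1: reproduce .93.** With k = 1, dose by time is detected in .94 (35 per arm) when read from the fit without dose × arm. With that term in the model and effect-coded it is .83. A logistic mixed model with a random child intercept (30 per arm) gives .83 with item noise and .98 with no added noise. The stated .93 is therefore attainable, but the match depends on noise and coding that the protocol does not state.

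**Step 2: power for the three-way term.** The last column is the share of trials in which dose by time is significant and the three-way term is not.

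| Per arm | k | Dose × time | Three-way | Dose credited over method |
|---|---|---|---|---|
| 35 | 1 | .94 | .06 | 88% |
| 35 | 1.67 | .97 | .21 | 77% |
| 35 | 2 | .98 | .35 | 64% |
| 30 | 1.67 | .94 | .20 | 75% |

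The reading barely distinguishes k = 1 (88%) from k = 1.67 (77%).

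**Step 3: sensitivity**

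- *Test point × treatment must also be null (dose centred):* 59–65% at k = 1.67 and 41–48% at k = 2. Taking the middle of the second range, this is about 45–65%.
- *No item noise, change score:* three-way power is .54–.75 over k = 1.67 to 2, but the same fit rejects in .12–.15 of runs at k = 1, so that power is inflated.
- *Logistic mixed model, 30 per arm (no added noise / item noise):* three-way power is 2% / 13% at k = 1.5 and 13% / 33% at k = 2. Dose is credited over method in 95% / 80% and 86% / 61%.
- *k = 3:* three-way power rises to .66–.71 (change score with item noise) or about .55 (mixed model).

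**Step 4: which ratio do the inputs imply?** Mean dose is the average of the four quartile midpoints.

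- Home recasts: (78 + 144 + 256 + 640)/4 = 279.5. Home stories: (150 + 350 + 710 + 1320)/4 = 632.5.
- Home gains are 4.0 − 3.0 = 1.0 and 5.5 − 3.0 = 2.5. Per exposure: 1.0/279.5 = .0036 and 2.5/632.5 = .0040, a ratio of about 0.9.
- Lab recasts: (414 + 840 + 936 + 984)/4 = 793.5. Lab stories: (414 + 849 + 945 + 960)/4 = 792.
- Lab gains are 8.0 − 3.0 = 5.0 ("M=8.0$ and $SD=3.5$ for the lab recasts condition ($ES=+2.0") and 6.0 − 3.0 = 3.0. At near-equal dose the ratio is about 5.0/3.0 = 1.67.

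**Step 5: confounding (assumption).** Dose is given no effect, but a hidden factor that drives gain correlates r with dose within arm (30 per arm). Dose by time is then significant in 7–52% of trials at r = .3 and 34–95% at r = .5, depending on model and noise, against a nominal 5%.

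**The case against.** The strongest reply has four parts.

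1. **The ratio.** Aim 2 uses only the home arms, whose inputs imply a ratio near 0.9, in line with the simulation's equal-benefit assumption. A reader might infer from the lab figures that the protocol expects a 1.67-fold difference at home. It does not, and Aim 1 hypothesises equally effective lab conditions. This stands: 1.67 is a scenario only. It does not rescue the sentence, because assuming equality is different from showing it.
2. **Aim 1 tests method at controlled dose.** True, so a per-exposure difference is not hidden from the whole trial. But Aim 2 states its own conclusion for caregiver delivery and does not make it depend on Aim 1.
3. **The stated rule includes test point × treatment.** Counting that term lowers the share to about 45–65%. A reader might infer that the trial will almost always credit dose over method; with this term, with low noise or at a 3-fold difference, that is too strong. However, the disputed sentence does not require the term to be null, and once dose is in the model its meaning depends on centring, which is not stated.
4. **Partial disclosure.** The power section admits that dose is confounded with delivery approach. The interpretation under Aim 2 is not limited accordingly.

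A reader might also infer that confounding by engaged families would produce a dose effect in most trials. The documents give no size for such confounding, and the range in step 5 is too wide to support that.

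**Conclusion.** The point holds as one of interpretation. The planned two-way term supports an association between exposures received and gain. It supports neither a causal dose claim nor the exclusion of a method difference. The .93 addresses neither issue, because its simulation contained no confounding and no per-exposure difference.

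With item noise and 30 to 35 children per home arm, a difference of 1.67- to 2-fold would be missed in most trials (three-way power about .2 to .3). Dose would be credited over method in roughly 65–75%, or about 45–65% under the stricter reading. These figures rest on assumed ratios, an assumed noise model and a simplified random-effects structure; low-noise change-score fits and larger differences give clearly higher power. The sentence should be corrected before analysis. The design and the model need not change.

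**What to change.** - Replace the sentence: a two-way interaction will be reported as an association between exposures received and gain, which does not by itself exclude a difference between methods.
- Report the dose slope in each home arm, and the three-way estimate or slope ratio with a 95% CI. Conclude that dose matters rather than method only if that interval excludes a per-exposure difference named in advance, and word even that as conditional on unrandomised dose.
- Make the randomised test point × treatment contrast, fitted without dose, the causal comparison of the home arms.
- State the three-way power for the named difference beside the .93, with the noise model used.

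The cost is some wording, two slopes and an interval from the model already planned, one simpler model fit and one extra simulation. The downside is a weaker Aim 2 claim, since the interval may be too wide to exclude the named difference.
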